### Collecting and recording AEs

We will be tracking all AEs and serious adverse events (SAEs) that a participant may experience once starting the study intervention (from Baseline onward). We will be doing this throughout the study, regardless of whether or not we think they are related to the study intervention. AEs will be documented by research personnel during research assessments, or at any other time during the clinical trial that they have contact with or about the subject. The PIs and study doctor are responsible for oversight on AEs.

We will document each AE with details such as:

- Description of event;
- Start and stop dates (if applicable);
- Whether or not they are getting treated (e.g. medications or therapies);
- Whether or not it is considered an SAE;
- Any other pertinent details.

Collected AEs will be documented and recorded with the information above on AE forms and entered into an electronic database (i.e., REDCap). On a weekly basis, the PI will review each AE to determine the following:

- Relationship to the study intervention;
- Severity of the event;
- Outcome;
- Status: ongoing, closed, lost to follow-up;
- Deciding what course of action should be taken to address the AE.

The PI may consult with the study physician if needed.

If the participant reports a SAE, the same collection and recording procedures will take place as with AEs. However, research staff will alert the PI to the SAE as soon as possible (within 24 hours of a reported SAE). The PI will review the reported SAE within 24 hours of becoming aware of it. SAEs will have a separate form completed for each one that's reported.

## 8.0. Data Analysis and Sample Size

### 8.1. Determination of Sample Size

Given that this is primarily a feasibility and acceptability trial, we expect the intervention effect sizes to have notable variance (i.e., wide confidence intervals), thus the relevance of the current study is linked to its significance and potential impact to the field, and not on its ability to estimate parameter estimates in the population. In this scenario, a precision (rather than power) approach is especially suited, since calculating confidence intervals is ideal for preliminary or pilot investigations, and facilitates that sample size is determined by practical rather than formal considerations. Given that retention is a key issue in smoking cessation studies, we will focus on this primary outcome. A pilot study of LTQ and prior studies in the general population of ACT-based interventions for smoking cessation show 93% 6-month participant retention, and 70% for standard of care.

Further, with 30 participants per group, we calculated that we would have 70%, 75% and 80% power to detect abstinence rates of 0.32, 0.34, and 0.36 effect sizes, respectively.

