## 2.0. Goals and Aims

### 2.1. Aims

The overarching goals of this phase of the research are to evaluate the feasibility, acceptability, and preliminary efficacy of a tailored smoking cessation app for PLWH, “Learn to Quit-HIV” or “LTQ-H” for short, which was iteratively developed in the first phase of research. Specifically, we propose to conduct a feasibility, acceptability, and preliminary efficacy trial comparing LTQ-H (n=30) to an app based on U.S. Clinical Practice Guidelines only (NCI QuitGuide; n=30) among HIV-positive smokers. NCI QuitGuide will match LTQ-H’s format of delivery, dose, and duration. Both apps will be integrated with NRT and ongoing HIV clinical care. Primary outcomes: feasibility (i.e., recruitment rates, retention, app engagement); acceptability (i.e., usability, user experience, perceived utility). Secondary outcomes: cigarettes smoked per day, quit attempts, biochemically verified abstinence, NRT adherence and participant safety. Successful execution of this aim will indicate the feasibility, acceptability, and preliminary efficacy of LTQ-H.

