## 4.0. Study Overview

- 1. Eligibility and Consent:** PLWH who provisionally qualify based on a phone screen will be invited to attend a remote Zoom screening visit. Informed consent will be obtained, and participants' interest in quitting, HIV and smoking statuses will be evaluated. Individuals will be screened to ensure that they own an Apple or Android smartphone, are not pregnant (if female), and are medically eligible to use NRT. Our study physician will evaluate their medical eligibility. In addition, we will obtain a signed Release of Information from potential participants to closely work with their own medical providers to monitor adverse events, dispensing of NRT, and overall participant safety.
- 2. Randomization:** Participants will be allocated to conditions using 1:1 randomization.
- 3. Interventions:** Participants will be assigned to LTQ-H or NCI QuitGuide. All participants will receive a standard 8-week course of NRT (transdermal nicotine patches starting at 21mg/24h) following recommendations contained in the U.S. Clinical Practice Guidelines.
- 4. Background Analytics:** Research staff will instruct participants on how to install the study app onto their personal smartphones and will tell them how to add a study ID in the app that will be used to retrieve background analytics information (Google Analytics) from both the LTQ-H and NCI QuitGuide apps.
- 5. Follow-Up Visits:** Visits will occur at 4, 8 and 12 weeks post-randomization. During these visits we will assess smoking and smoking abstinence, new or changes in existing adverse events and user experience with the assigned app. We will biochemically verify self-reported smoking abstinence at week 12.

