#### Secondary outcome measures include:

- Change in cigarettes smoked per day (CPD) (measured daily with the tracking feature embedded within each app)

- Quit attempts (self-reported no smoking at all for 24 hours—and *time to 7-day relapse* will be assessed via a Timeline Follow Back interview at Weeks 4, 8, and 12)
- 7-day point prevalence abstinence (not smoking even a puff of a cigarette within the last 7 days) and breath CO<5 ppm at Weeks 4, 8, and 12)
- Adherence to NRT (measured via app tracking feature and Timeline Follow-Back interview at Weeks 4, 8, and 12)
- Participant safety (adverse events)

Differences between treatment groups (LTQ-H vs. NCI QuitGuide) in terms of secondary outcomes will be assessed via chi-square tests and logistic regression or t-tests and linear regression, as appropriate:

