**Chi-square tests and logistic regression:**

- Quit attempts (prevalence of any quit attempts, yes/no)
- 7-day point prevalence abstinence (prevalence of any verified abstinence, yes/no)
- Adherence to NRT (prevalence of use of optimal amount of NRT, yes/no)
- Participant safety (prevalence of any adverse events, yes/no)

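### Is the power sentence in section 8.1 wrong because it never says what 0.32, 0.34 and 0.36 measure?

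*Combined protocol and SAP*

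**What the plan says.** Section 8.1 first explains how the trial was sized. It holds that for a pilot "a precision (rather than power) approach is especially suited", that the number of participants follows from practical grounds, and that retention is the outcome in focus. It cites earlier studies that "show 93% 6-month participant retention, and 70% for standard of care".

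One further sentence then turns to abstinence: "with 30 participants per group, we calculated that we would have" is followed by "70%, 75% and 80% power to detect abstinence rates of 0.32, 0.34, and 0.36 effect sizes, respectively". No significance level, sidedness, test or QuitGuide abstinence rate is given there, and no other section supplies a level or a rate.

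The test can be found elsewhere. Section 8.2 states that differences between the arms "in terms of secondary outcomes will be assessed via chi-square tests and logistic regression or t-tests and linear regression, as appropriate", and its list for chi-square tests and logistic regression includes "7-day point prevalence abstinence (prevalence of any verified abstinence, yes/no". Section 2.1 sets the rank of the outcome: "Secondary outcomes: cigarettes smoked per day, quit attempts, biochemically verified abstinence, NRT adherence and participant safety". Section 4.0 gives the allocation: "Participants will be allocated to conditions using 1:1 randomization".

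**The concern.** An abstinence rate belongs to one arm; an effect size compares two. A sentence that uses both names for the same numbers does not say what the trial could detect. Taken literally, it invites a reader to treat 36% as the LTQ-H abstinence rate that the trial would detect with 80% power. Whether that holds depends wholly on the QuitGuide rate, which is not given.

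The stake would be a misjudged detectable effect. Someone who pictured 36% against 20% would believe that power is 80% when it is about 28%. The timeline in section 4.1 foresees an application for a larger randomised trial, so a misread figure could carry over into planning.

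**Working it through.** **Inputs.** From the documents: 30 per arm (section 8.1), so N = 60; 1:1 allocation (section 4.0); chi-square test for binary abstinence (section 8.2); printed powers of 70%, 75% and 80% at 0.32, 0.34 and 0.36 (section 8.1). Assumed, because the documents are silent: two-sided 5% level, no continuity correction, all 60 analysed. QuitGuide rates below are scanned values, not figures from the plan.

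**1. Cohen's w.** For a 1-df chi-square test the noncentrality is N × w², and power is very nearly Φ(√(N × w²) − 1.96).

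| w | N × w² | square root | minus 1.96 | power | printed |
|---|---|---|---|---|---|
| 0.32 | 60 × 0.1024 = 6.144 | 2.479 | 0.519 | 69.8% | 70% |
| 0.34 | 60 × 0.1156 = 6.936 | 2.634 | 0.674 | 75.0% | 75% |
| 0.36 | 60 × 0.1296 = 7.776 | 2.789 | 0.829 | 79.6% | 80% |

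All three printed powers are reproduced to the nearest percent.

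**2. Absolute difference in abstinence.** With equal arms, w = |p1 − p2| / (2√(p̄(1 − p̄))), where p̄ is the mean of the two rates. The denominator is at most 1, reached at p̄ = 0.5, so w is never below the difference. Example: a 36-point difference from a QuitGuide rate of 10% is 10% against 46%, with p̄ = 0.28 and w = 0.36 / 0.898 = 0.401, giving 87% power. Power for differences of 32, 34 and 36 points:

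| QuitGuide rate (assumed) | power |
|---|---|
| 5% | 86 / 89 / 91% |
| 10% | 81 / 84 / 87% |
| 15% | 76 / 81 / 84% |
| 20% | 73 / 78 / 82% |
| minimum over all rates | 69.8 / 75.0 / 79.6% |

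The printed values are therefore a floor on this reading. Under Fisher's exact test or a continuity-corrected test the minimum falls to 62 / 68 / 74%.

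**3. LTQ-H abstinence rate.** The same formula for w applies with the LTQ-H rate held at 32%, 34% or 36%. Example: 36% against 10% has p̄ = 0.23, w = 0.26 / 0.842 = 0.309, √60 × 0.309 = 2.39, and power Φ(0.43) = 67%.

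| QuitGuide rate (assumed) | power |
|---|---|
| 5% | 77 / 81 / 85% |
| 7% | 69 / 74 / 78% |
| 10% | 55 / 61 / 67% |
| 15% | 34 / 40 / 46% |
| 20% | 19 / 23 / 28% |

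The printed powers need a QuitGuide rate of about 7% or lower. The threshold is 4.3% to 7.9% across two-sided methods and 9.2% to 10.2% with a one-sided 5% level.

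**4. Cohen's h or d.** Power would be 23% to 29%, far from 70% to 80%. The printed powers themselves exclude this reading.

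**5. What w = 0.36 means in rates.** Solving the formula gives, for QuitGuide against LTQ-H, about 10% against 41%, 15% against 49%, or 20% against 55%.

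**6. Attrition.** If the cited retention applied at 12 weeks and losses left the denominator, 0.93 × 30 + 0.70 × 30 = 27.9 + 21 = 48.9, or about 49 analysed. Power at the three values of w would then be 61 / 66 / 71%. Both conditions are assumptions: the cited retention is at 6 months and from other studies.

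**The case for a change.** The best case for a change is that w is recovered only by back-calculation. The label appears nowhere, and a match is not proof of origin: by the pooled normal formula, one QuitGuide rate of about 7% would also reproduce all three powers with the values as LTQ-H rates. The literal wording leans towards a rate, and w = 0.36 stands for a much larger contrast than 36% suggests. The protocol chose to print a power claim, tests on abstinence are planned, and one sentence would settle the matter.

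Much of this stands. The wording is unclear, and a reader planning a later trial should not lift the 0.36 without asking what it is. What does not follow is that the plan's figure is wrong. The reading under which power falls short needs a QuitGuide rate above the threshold, and the documents give no such rate. The reading that uses the planned test and the full 60 matches every printed figure. Nor is the repair quite free: a sentence that says all 60 are analysed and that the test is uncorrected would commit the analysis to choices the plan has not recorded.

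**Conclusion.** This is a reporting gap and not an arithmetic error. At an assumed two-sided 5% level, with an uncorrected chi-square test and all 60 participants analysed, the printed 70%, 75% and 80% agree with Cohen's w to within half a percentage point, and they are a lower bound if the values are absolute differences. They would overstate power only if the values were LTQ-H rates and QuitGuide abstinence exceeded roughly 7% (about 9% to 10% with a one-sided 5% level), or if a conservative test or loss of participants from the denominator applied.

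Nothing in the trial rests on the sentence. The sample size comes from precision and practical grounds, the primary outcomes are reported descriptively or by thematic analysis, and abstinence is a secondary outcome whose planned test is the same whichever meaning was intended. Naming the metric and the level would make the sentence easier to read but would leave the design, the analysis and the conclusions as they are. No change is called for.

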### 8.2. Data Analysis

#### Primary feasibility outcomes include:

- Recruitment rates and participant retention;
- App engagement (frequency and duration of app use)

We will report on *recruitment rates and participant retention* descriptively. Trajectories of *app engagement* will be plotted to examine ongoing *interactions with the app* and *duration of app use* per day.

#### Primary acceptability outcomes include:

- App usability (System Usability Scale);
- User experience (semi-structured interviews);

Acceptability outcomes will be evaluated descriptively with summary scores of the SUS. Scores above the SUS threshold (>68) are considered optimal. User experience will be extracted via Thematic Analysis of transcripts of semi-structured interviews.

#### Secondary outcome measures include:

- Change in cigarettes smoked per day (CPD) (measured daily with the tracking feature embedded within each app)

- Quit attempts (self-reported no smoking at all for 24 hours—and *time to 7-day relapse* will be assessed via a Timeline Follow Back interview at Weeks 4, 8, and 12)
- 7-day point prevalence abstinence (not smoking even a puff of a cigarette within the last 7 days) and breath CO<5 ppm at Weeks 4, 8, and 12)
- Adherence to NRT (measured via app tracking feature and Timeline Follow-Back interview at Weeks 4, 8, and 12)
- Participant safety (adverse events)

Differences between treatment groups (LTQ-H vs. NCI QuitGuide) in terms of secondary outcomes will be assessed via chi-square tests and logistic regression or t-tests and linear regression, as appropriate:

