### 4.1. Timeline

	Sep 2019 - Aug 2020												Sep 2020 - Aug 2021												
	YEAR 1						YEAR 2																		
	SEP	OCT	NOV	DEC	JAN	FEB	MAR	APR	MAY	JUN	JUL	AUG	SEP	OCT	NOV	DEC	JAN	FEB	MAR	APR	MAY	JUN	JUL	AUG	
Aim 2: Pilot Randomized Controlled Trial of LTQ-H App																									
Obtain human subjects approval (full board, medical oversight and health outcomes)					X	X	X	X																	
Recruitment through Duke MyChart and community advertisement								X	X	X	X	X	X	X	X	X									
Data collection for pilot randomized controlled trial (n = 60)							X	X	X	X	X	X	X	X	X	X	X	X	X	X	X				
Complete data analysis and prepare article for publication																						X	X	X	X
Prepare NIH submission for R01 randomized controlled trial																						X	X	X	X

Participants who are enrolled in Phase 2 of the study will participate over the course of 12 weeks, which includes a screening visit, randomization visit, plus 3 monthly follow-up visits.

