#### 6.4. Follow-Up Visits

Participants will complete monthly follow-up (FU) visits at Weeks 4, 8, and 12 weeks post-randomization. All visits will be conducted via zoom video calling.

At each visit, participants will complete surveys to assess their smoking behavior, changes in physical or mental health (which will prompt staff to assess for adverse events), and user experience with their assigned study app. See table below for a list of all the measures.

At each visit, research staff will conduct an interview with the participant to ask about their experience using their assigned app. This interview will be audio recorded for later review. Each FU visit is expected to last between 45-60 minutes, depending on the assessment burden.

Measure	Week 4	Week 8	Week 12
Biochemical Verification (CO)			x
Health Changes Questionnaire	x	x	x
Adverse Events and Con Meds (if applicable)	x	x	x
COVID-19 & Quitting Smoking Questionnaire (Follow-up)	x	x	x
Drug Use Questionnaire (1 Month)	x	x	x
Timeline Follow-Back	x	x	x
DASS-21	x	x	x
BSI	x	x	x
Systems Usability Scale (SUS)	x		x
Qualitative user experience interview	x		x
Research Participant Perception Survey (RPPS)			x

Participants who self-report smoking abstinence by the final follow-up visit (FU3) will be mailed an iCO smokerlyzer device to do a breath test in order to biochemically verify abstinence. We will mail these to participants following their FU3 session. Once they receive the device, we will set up a short Zoom call to walk them through the CO breath test process. Staff will be on the call in order to ensure that it is the participant

who is doing the test, and that they are doing the test properly. Once the participant completes the test, we will ask them to email the result of their test to our lab email. Participants will keep these devices once they are completed in the study. The stop date for these participants will be the date of this breath test instead of the date of the FU3 visit.

Background analytics will be collected throughout the 4 months of participation, and will be measuring some things such as CPD, mood ratings, NRT use, duration of app use, and number of interactions within the app.

At the final visit (Week 12), participants will be given quitting resources if they have not quit. They will also be referred to other research studies, if eligible and willing.

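### Section 8.2 defines CO-verified abstinence at Weeks 4, 8 and 12, but CO is planned for Week 12 only, and that test falls after the self-report it is meant to verify

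*Combined protocol and SAP*

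**What the plan says.** The analysis section (8.2, secondary outcome measures) lists 7-day point prevalence abstinence as a negative self-report "and breath CO<5 ppm at Weeks 4, 8, and 12". The list of chi-square and logistic analyses in 8.2 then uses a yes/no variable for any verified abstinence, without naming a time point.

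The other sections give one CO time point. Section 2.2, secondary outcome 3, attaches the CO criterion to Week 12. Section 4.0, item 5, verifies at Week 12. Section 5.2 places the breath test at the Week 12 visit and sends devices only to those who report abstinence. The table in 6.4 marks CO under Week 12 alone.

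The text of 6.4 then describes a later test. On the devices it says: "We will mail these to participants following their FU3 session". Next: "Once they receive the device, we will set up a short Zoom call to walk them through the CO breath test process". The one item it asks participants to return is the reading: "Once the participant completes the test, we will ask them to email the result of their test to our lab email". It closes with: "The stop date for these participants will be the date of this breath test instead of the date of the FU3 visit".

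Section 8.1 states 70%, 75% and 80% "power to detect abstinence rates of 0.32, 0.34, and 0.36 effect sizes"; abstinence is the only outcome given a power figure.

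**The concern.** There are two problems with one outcome.

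First, an analyst working from 8.2 would look for CO results at three visits and find them for one. Because the tested variable has no time point, 8.2 read alone suggests abstinence verified at any of three visits. That is a different quantity from abstinence verified at Week 12.

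Second, even at Week 12 the two halves of the definition come from different dates. A participant who truthfully reports abstinence at FU3 and smokes before the call can fail CO. A participant who reports falsely at FU3 and stops before the call can pass.

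At stake is the meaning of the trial's only biochemically checked efficacy outcome. It is secondary, but it is compared between arms, so it needs a single definition that the schedule can supply.

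**Working it through.** **1. The plan's own figure.** Inputs from 8.1 are 30 per group, so N = 60, and effect sizes 0.32, 0.34 and 0.36. Section 8.1 gives neither the metric nor alpha. Assume Cohen's w, a chi-square test with 1 degree of freedom and two-sided alpha 0.05. Power is then approximately Φ(√N × w − 1.96), with √60 = 7.746:

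- w = 0.32: Φ(2.479 − 1.96) = 69.8% (stated 70%)
- w = 0.34: Φ(2.634 − 1.96) = 75.0% (stated 75%)
- w = 0.36: Φ(2.789 − 1.96) = 79.6% (stated 80%)

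The figures reproduce under these assumptions. They use no CO time point, so this point does not alter them.

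**2. CO time points, side by side.**

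| Place | CO time point |
|---|---|
| 2.2, secondary outcome 3 | Week 12 |
| 4.0, item 5 | Week 12 |
| 5.2, breath test | Week 12 visit |
| 6.4, table | Week 12 column only |
| 6.4, text | call after FU3 |
| 8.2, secondary outcomes | Weeks 4, 8 and 12 |

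Time points without CO data: 3 − 1 = 2. Readings per participant: 1 if the participant reports abstinence and is tested, otherwise 0, against 3 implied by 8.2. Since devices leave only after FU3, no participant has a study device at Week 4 or 8. The variable for any verified abstinence therefore reduces to Week 12.

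**3. Why the two readings of 8.2 differ.** This is an illustration with assumed rates; the documents give none. With a verified rate p at each visit, verification at any of three visits has rate p if the same people are abstinent each time, and 1 − (1 − p)³ if visits are independent.

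- p = 10%: 10% to 1 − 0.9³ = 27.1%, against 10% for Week 12 alone
- p = 20%: 20% to 1 − 0.8³ = 48.8%, against 20%

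**4. Timing at Week 12.** FU3 on schedule is day 12 × 7 = 84 after randomization, and its self-report covers the 7 days up to then. The device is mailed afterwards, so the test is on day 84 + d with d > 0. Section 6.4 gives no upper limit for d. The 7 days before the test share 7 − d days with the FU3 window, and none once d reaches 7. The Timeline Follow-Back for Week 12 is done at FU3, so it does not cover the gap. No value of d is given, so the number of participants misclassified cannot be derived.

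**The case against.** The strongest reply is that 8.2 contains a drafting slip. It stands alone against four other places, its closing parenthesis is unbalanced, and the list of weeks repeats that of the neighbouring bullets. This is fair, and it settles which text to correct. It does not make the text right: as written, the weeks follow the CO criterion, and the tested variable names no time point.

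On timing, 6.4 is open about the later test and moves the stop date to match. Mailing a device is a reasonable choice in a remote pilot. That no 7-day question is repeated rests on silence, since 6.4 describes the call only briefly. Both remarks stand. What remains is the conflict between 5.2 and 6.4, and a definition that does not say which date it describes.

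A reader might infer more than the documents support:

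- **Lost data at Weeks 4 and 8.** No CO was ever scheduled then, so the count of two describes the definition, not missing readings.
- **A test outside the participation period.** Section 4.1 speaks of 12 weeks, but it includes the screening visit in them, while FU3 is counted from randomization. Section 6.4 itself refers to 4 months. The 12 weeks are nominal and cannot carry this argument.
- **Bias between arms.** The CO procedure is the same in both arms, and nothing in the documents points to a differential effect.
- **A hard cut-off for late tests.** This could turn a mailing delay into a failed verification and add misclassification of its own.

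**Conclusion.** The point holds as a definition that the schedule cannot supply and a timing conflict between sections. Verified abstinence cannot be derived at two of the three time points in 8.2; only Week 12 is available, with 0 or 1 reading per participant. At Week 12 the reading is taken after the 7 days reported at FU3, with no stated limit on the delay, and errors can go either way.

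This rests on two assumptions: that a CO reading reflects smoking near the test date, and that the call includes nothing beyond what 6.4 describes. The frequency of misclassification is unknown and no effect size is claimed. The feasibility and acceptability outcomes and the power figures in 8.1 are unaffected. It should be fixed because the outcome is tested between arms and the correction is cheap.

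**What to change.** 1. In 8.2, attach the CO criterion to Week 12 only, and rename the binary variable as verified 7-day abstinence at Week 12. Label any abstinence reported for Weeks 4 or 8 as self-report only.
2. In 5.2, say as 6.4 does that the breath test takes place on a call after FU3.
3. Repeat the 7-day question on that call. State that verified abstinence requires all three: abstinence reported at FU3, abstinence on the repeated question, and CO below 5 ppm on the test date. This settles which report governs when the two differ. Someone who relapses after FU3 is still not verified, but by a stated rule.
4. State that a participant who reports abstinence but has no CO result counts as not verified.
5. Give a target interval from FU3 to test, set by the study team from its mailing time. Report the actual delay by arm, and show results with late tests included and with them excluded. Do not fail late tests automatically.

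The cost is wording in 5.2, 6.4 and 8.2, one question on a call already planned, and one sensitivity analysis. The drawback is that participants who report abstinence are classified slightly later than the FU3 date used for the others. If follow-up has already ended, the question can no longer be added. The wording can still be corrected, and the delay should be obtainable because the stop date is defined as the test date.
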